4 STUDY POPULATION AND STUDY PROCEDURES

4.1 Inclusion and exclusion criteria, justification of study population

Power analysis was conducted with G*power to determine participants numbers (n) calculating a treatment effect size of 0.46 from previous research with the comparable MedX ILEX device in healthy volunteers (Fisher et al., 2018). The priori sample size was calculated ($\alpha = 0.05$; effect size = 0.46; test family = F test, and statistical test = analysis of variance (ANOVA) repeated measures, within-between interaction; number of groups = 2; number of measurements = 3; power = 0.8) and revealed $n = 10$ participants. 14 healthy volunteers will be recruited according to the following criteria:

Study inclusion criteria:

- Healthy (no acute musculoskeletal injuries or illness),
- Pain free,
- Sufficient understanding of the German language,
- Able to give informed consent as documented by signature,
- Between 18 and 50 years old

Study exclusion criteria:

- Pregnant (urine pregnancy test is given to participating woman) or lactating women,
- Medication,
- Previous surgery in the lumbar spine,
- Knee or hip disorders contraindicating the use of ILEX device,
- Currently experiencing LBP,
- History of LBP or lumbar spine pathologies or known deformities,
- Psychological or neuromuscular disorders, spinal pathologies or any other injuries or illness that would restrict normal movement,
- Previous (last 12 months) or current isolated training of the lumbar extensor.

This study will be conducted in healthy people. The risk of injury will be low in this population group.

4.2 Recruitment, screening and informed consent procedure

Participants will be recruited on the websites of the physiotherapy schools Thim van der Laan (www.physioschule.ch) and University of Applied Sciences of Southern Switzerland SUPSI (www.supsi-landquart.ch). An electronic advertisement will be activated on the screens in the building of the Thim van der Laan AG in Landquart. The advertisement texts are in line with the guidelines published by the Zurich Cantonal Ethics Committee.

During the initial contact, potential participants are informed about the procedure and risks of the study, as well as the conditions and the amount of compensation. A checklist is used as the basis for telephone contact. During the first telephone contact, a questionnaire will be completed by the investigator to assess suitability for participation in the study.

The investigators will explain to each participant the nature of the study, its purpose, the procedures involved, the expected duration, the potential risks and benefits and any discomfort it may entail. Each participant will be informed that the participation in the study is voluntary and that he or she may withdraw from the study at any time and that withdrawal of consent will not affect his or her subsequent medical assistance and treatment.

The participant will be informed that his or her medical records may be examined by authorised individuals other than their treating physician.

All participants for the study will be provided a participant information sheet and a consent form describing the study and providing sufficient information for participant to make an informed decision about their participation in the study. Enough time will be given to the participant to read the written informed consent at home, ask questions to the responsible examiner and decide whether to participate or not.

The formal consent of a participant, using the approved consent form, will be obtained before the participant is submitted to any study procedure.

The consent form will be signed and dated by the investigator or his designee at the same time as the participant sign. A copy of the signed informed consent will be given to the study participant. The consent form will be retained as part of the study records. The original signed informed consent form will be stored as a study document in a locked filing cabinet.

Upon successful completion of the training sessions and the 3 test days, the participants are receiving a remuneration of 200 Swiss Francs.

The advertisements, questionnaire, and checklist for the first contact can be found in the enclosure.

4.3 Study procedures

A table listing all study visits, relevant procedures, as well as all timelines, can be found in

appendix 1.

12 sessions of back extensor resistance training on the ILEX machine take place over a 6-week period (twice a week). Before each exercise, a diathermy treatment is taking place. Before, after 6 sessions and after completion of the 12 sessions, tests are conducted on separate days.

On intervention days, the participants enter the RES laboratory in Landquart wearing sports clothing. First, they lay on an examination table in a prone position receiving a treatment with the diathermy device for 10 minutes from a trained examiner. The intervention group is treated with the diathermy device inducing 448kHz capacitive monopolar radiofrequency, warming up the deep tissues. The sham group receives a massage with the diathermy device without radiofrequency. Directly after the first and last diathermy treatment, a picture will be taken with an infrared camera (FLIR A600 series, Emitec Industrial, Rotkreuz, Switzerland). Then, participants translocate to the ILEX machine and are seated according to their individual settings. The training session lasts 12 minutes. Participants begin the training session with a dynamic warm-up of the lumbar extensor for 120s, followed by three sets of resistance training lasting 120s, 120s, and 150s respectively, and concluding with a final set of dynamic recovery lasting 60s. Between each set, a 30-second recovery is provided. Repetitions will be executed by taking three seconds from complete flexion to complete extension, ensuring standardization at 20 repetitions per minute. A metronome with 40 beats per minute will provide audible feedback. The ILEX machine emits an audible signal upon completion of each phase of the repetition to guarantee a complete ROM is achieved. A low load is used for the warm-up and recovery. For the three training sets, the initial load is based on the maximal isometric force and subsequently increased until volitional fatigue. Immediately subsequent to each training session, participants will be requested to provide their effort (RPE-E) and discomfort (RPE-D) values. Immediately after the first and final diathermy treatment before dislocating to the ILEX machine, participants skin temperature is measured while laying prone on the examination table making an imaging with the FLIR camera.

On the examination days (BL, F/U1 and F/U2), the participants enter the RES laboratory in Landquart wearing sports clothing. At baseline, participants are asked to sign an informed consent form and are screened for inclusion and exclusion criteria. Participants are then asked for their age and sex, height is measured using a stadiometer (GPM Stadiometer, Zurich, Switzerland), and weight and lower body fat percentage are measured using a scale (TANITA-TBF 611 scale, Tokyo, Japan). At all three measurements (BL, F/U1 and F/U2) participants are asked to complete the IPAQ to assess physical activity. Next participants are placed on the examination table in a prone position for an ultrasound scan to measure the thickness of the M. erector spinae on the right side. The probe head is coated with coupling gel and applied perpendicular to the muscle on the right side without pressure to not compress the dermal surface. The images are saved, and the distance is measured later. Participants are then familiarised with the ILEX machine and positioned for individual adjustments. After a warmup for 120s with a low load and a short break, participants are asked to move dynamically into full flexion and full extension over the full ROM for three times. The test is repeated a second time. After a 2-minutes break, participants are asked to slowly move backwards to maximal tension and repeat the isometric force test after 2-minutes break. Next, the participant is seated in front of the sit-and-reach test box keeping the knees fully extended and the feet dorsiflexed against the foot-support. The participant is moving actively, slowly forward, bringing the body to the pain-free limit. The participant's hands move along the scale on the block until the movement is terminated because the participant can go no farther. The final position is held with an isometric contraction for 2 seconds, and the distance is read on the scale. After a 2-minutes break, the test is repeated. The rating scales for perceived effort, discomfort and thermal sensation are then presented for familiarization. Finally, the isometric back extension endurance is measured through the Biering-Sørrensen test. The participant is lying prone on an examination table with the upper border of the iliac crests in line with the edge of the table. The lower body is secured to the table by three straps around the pelvis, knees, and ankles. With the arms folded across the chest, the participant is asked to hold the upper body isometrically in a horizontal position. A stopwatch is used to measure the time the participant can keep the unsupported upper body in contact with a horizontal object. The examination takes about 1 hour.

Withdrawal and discontinuation

Participants can withdraw from the study at any time without giving a reason. Previous research has shown that training the back extensor muscles with ILEX machines once a week is as effective as training two or three times a week for increasing isometric lumbar extension strength (Carpenter et al., 1991; Graves et al., 1990). Missed training sessions are analysed on a case-by-case basis to decide whether to withdraw from the study. Participants will be withdrawn from the study if an impending injury or illness contraindicates the use of the ILEX device. For scientific and economic reasons, data already collected are included in the analyses as far as possible.

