3 STUDY OBJECTIVES AND DESIGN

3.1 Hypothesis and primary objective

The main aim of this study is to investigate the effect of back extensor strength after 6 weeks of ILEX training and diathermy therapy.

- H_0 : 6 weeks of resistance training on the ILEX machine does not improve lumbar extensor muscle strength.
- H_1 : 6 weeks of resistance training on the ILEX machine improves the strength of the lumbar extensor muscle.
- H_0 : There is no difference in the improvement in lumbar extensor muscle strength between those who receive a microwave diathermy treatment before each resistance training session and those in the sham group.
- H_1 : Individuals who receive a microwave diathermy treatment prior to each resistance training session improve their lumbar extensor muscle strength more than those in the sham group.

Secondary objectives are to examine the development of M. erector spinae thickness, isometric back extension endurance, and lumbar extensor flexibility after 6 weeks of resistance training and diathermy therapy.

- H_0 : 6 weeks of resistance training on the ILEX machine does not enhance the thickness of the M. erector spinae.
- H_1 : 6 weeks of resistance training on the ILEX machine enhances the thickness of the M. erector spinae.
- H_0 : There is no difference in the increase of the thickness of the M. erector spinae between those who receive a microwave diathermy treatment before each resistance training session and those in the sham group.
- H_1 : Individuals who receive a microwave diathermy treatment prior to each resistance training session enhance the thickness of the M. erector spinae more than those in the sham group.
- H_0 : 6 weeks of resistance training on the ILEX machine does not improve isometric back extension strength endurance.

- H_1 : 6 weeks of resistance training on the ILEX machine improves isometric back extension strength endurance.
- H_0 : There is no difference in the improvement of the isometric back extension strength endurance between those who receive a microwave diathermy treatment before each resistance training session and those in the sham group.
- H_1 : Individuals who receive a microwave diathermy treatment prior to each resistance training session improve the isometric back extension strength endurance more than those in the sham group.
- H_0 : 6 weeks of resistance training on the ILEX machine does not increase lumbar ROM.
- H_1 : 6 weeks of resistance training on the ILEX machine increases lumbar ROM.

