3.3 Study design

This is a monocentric clinical trial with minimal risks and burden of the risk class A (KlinV, Art. 20). A block randomization with covariates (i.e. sex) is used. The preheating is done as a single blinded randomized controlled trial (RCT) with the sham group receiving a 10-minute diathermy treatment with the Tecar device turned off and not sending radiofrequency before each exercise session. The intervention group undergoes a 10-minute treatment with the Tecar device to induce 448kHz capacitive monopolar radiofrequency and facilitate warming up of deep tissues. In order to be able to carry out a single-blind situation as far as possible, the test subjects are not told that the therapy causes heat of the deep tissue and that this is the factor being investigated. Instead, we speak of high-frequency Tecar therapy and its known use to promote tissue healing processes.

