8.2 Data recording and source data

For this study, all data will be reported in the paper CRF and translated into a Microsoft Excel file (Version 16.79 (2023), Microsoft Corporation, Redmond, Washington, USA). Maximum isometric force and ROM of the back extensor are both automatically saved in Microsoft Access (Version 6_4, Microsoft Corporation, Redmond, Washington, USA), translated to the CRF and exported to Microsoft Excel. The image of the M. erector spinae, generated through the ultrasound system Mylab2 (Esaote, Maastricht, Netherlands), is exported to the software HorosTM (Horos Project, Annapolis, MD, USA). The result of measuring the muscle thickness is reported on the CRF file and entered into Microsoft excel. Epidemiologic data, inclusion and exclusion criteria, measurements of the sit-and-reach test, Biering-Sørrensen test, ratings of perceived effort, discomfort, thermal sensation, and comfort, and details of each training session are recorded directly on the CRF and transferred to Microsoft Excel.

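### Erector spinae thickness is read later from saved ultrasound images with no step that hides arm or visit from the reader, so the plan allows an unmasked reading of its only structural endpoint

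*Combined protocol and SAP*

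**What the plan says.** Section 3.3 calls the diathermy comparison a "single blinded randomized controlled trial (RCT") and explains the blinding through what participants are told: "the test subjects are not told that the therapy causes heat of the deep tissue". No other role is described as blinded there or elsewhere. Under section 4.3, participants lie prone, "receiving a treatment with the diathermy device for 10 minutes from a trained examiner"; the device is active in one arm and emits no radiofrequency in the other.

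Thickness is scanned at BL, F/U1 and F/U2. Section 4.3 then says "The images are saved, and the distance is measured later". Section 3.2 defines the measurement as a distance between a point on the posterior fascia and a point on the L3 transverse process. Section 8.2 has the images exported to the Horos software, after which "The result of measuring the muscle thickness is reported on the CRF file and entered into Microsoft excel". The same section puts thermal-sensation ratings and training details on the CRF and into Excel. Section 8.3 codes the data by participant number, as a confidentiality measure.

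On the endpoint's role, section 3.1 states: "Secondary objectives are to examine the development of M. erector spinae thickness, isometric back extension endurance, and lumbar extensor flexibility". Two hypothesis pairs there rest on thickness. One is that training increases it. The other is that diathermy recipients "enhance the thickness of the M. erector spinae more than those in the sham group".

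**The concern.** Finding two anatomical points on an ultrasound image takes some judgement, and judgement can drift towards the expected answer if the reader knows which arm or visit the image comes from. The plan already separates scanning from measuring, which makes masked reading easy, but it does not use that separation.

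Both thickness hypotheses are exposed. Knowledge of arm can bias the diathermy-versus-sham comparison. Knowledge of visit can bias the training comparison, which has no untrained control because both arms train, so a reading bias between baseline and F/U2 cannot be told apart from a training effect. Section 3.2 also uses thickness, together with the Biering-Sørensen test, to corroborate the strength result. A biased reading would therefore lend false support to it.

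**Working it through.** **Does any section mask the reader?**
- Section 3.3: blinding is described for participants only.
- Section 4.3: the examiner who treats works with the device on or off, so can know the arm. Images are measured after the visit, by a person who is not named.
- Section 8.2: the pathway is image, export, measurement, CRF, Excel. No step removes identity, date or visit, and no reading order is set.
- Section 8.3: a participant number does not hide visit, and does not hide arm from staff who treated that participant. The Excel file is open to the laboratory team.

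No section supplies masking, and no section says that the reader is unmasked.

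**The plan's own figure.** Section 5.1 gives n = 10 (f = 0.46, alpha 0.05, 2 groups, 3 measurements, power 0.8). The correlation and sphericity settings are not stated; I assume 0.5 and 1. The noncentrality is then λ = f² × N × 3 / (1 − 0.5). For N = 10, λ = 0.2116 × 10 × 3 / 0.5 = 12.70 on (2, 16) df, and power is 0.833. For N = 8, power is 0.709. So n = 10 reproduces. It was derived from a strength-training study and has no bearing on masking.

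**How much would a reading bias matter?** The documents give no SD, reliability or expected change for thickness, so bias *b* is expressed in SDs of individual change from baseline to F/U2 and varied over an assumed range. Other inputs: 14 participants (section 3.4), 7 per arm (assumed, as the ratio is not stated), two-sided 5% level, no true effect.

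1. Arm-related bias, two-sample t-test on change. Noncentrality = b × √(7/2), 12 df, critical value 2.179.
2. Arm-related bias, planned three-visit interaction, with bias of 0, b/2 and b at the three visits and sphericity. The arm difference, centred over visits, is (−b/2, 0, b/2), so each arm departs by (∓b/4, 0, ±b/4). This gives λ = 14 × 2 × (b/4)² × 2 = 3.5b². The last factor 2 arises because the variance of change is twice the within-participant error variance. F on (2, 24) df, critical value 3.403.
3. Visit-related bias, paired t-test of baseline against F/U2 in all 14. Noncentrality = b × √14, 13 df, critical value 2.160.

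| b (SD of change) | 1. Noncentrality | 1. False-positive rate | 2. λ | 2. False-positive rate | 3. Noncentrality | 3. False-positive rate |
|---|---|---|---|---|---|---|
| 0.25 | 0.468 | 7.2% | 0.219 | 6.5% | 0.935 | 14.0% |
| 0.5 | 0.935 | 13.9% | 0.875 | 11.3% | 1.871 | 41.0% |
| 1.0 | 1.871 | 40.6% | 3.5 | 33.0% | 3.742 | 93.2% |

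For a bias of given size, the before-after comparison is the more exposed, because it uses all 14 participants and has no contrast in which a shared bias cancels.

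**The case against.** The strongest reply is that the documents are silent on the reader. A colleague might infer from single-blind status plus later measurement that the images will be read by someone who knows the allocation. The text does not support that. No reader is named, none is said to be the treating examiner, and the single-blind statement concerns how the preheating is delivered. Measuring later from stored images is also not a fault. This part of the reply stands, and it limits the point to what the plan permits.

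Three further replies stand in part:
- The landmarks are fixed anatomically in section 3.2, which narrows the reader's discretion. How far is unknown, because no reliability figure is given.
- Thickness is one of several secondary endpoints. It should not be read as the trial's main evidence, and nothing here touches the reading of the primary endpoint.
- The bias sizes are scenarios. Nothing in the documents shows that 1.0 SD, or any other value, is likely, and the planned interaction test gives somewhat lower figures than the t-test when the bias grows linearly.

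None of this supplies a masking step.

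**Conclusion.** The point holds as a missing safeguard on one secondary endpoint: a team could follow the plan exactly and still have thickness read by someone who knows arm and visit. Two hypothesis pairs depend on that reading.

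The size is conditional. If a reader's bias were half an SD of change, the nominal 5% error rate would rise to about 11% to 14% for the arm comparison, depending on the test, and to about 41% for the before-after comparison. At a quarter of an SD the figures are about 6.5% to 7% and 14%. These rest on the assumed bias, on 7 per arm, on sphericity and linear growth for the interaction test, and on no true effect. They show what is at stake and do not estimate a bias that has occurred. Stating the safeguard is worthwhile because it is cheap and must be in place before reading starts: a reader who has seen arm or visit cannot be made unaware of it.

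**What to change.** Add to sections 4.3 and 8.2:
- An existing team member other than the reader, or a script whose key the reader cannot open, exports each image under a random code that carries no participant number, arm, date or visit.
- All images are measured in random order after the last F/U2.
- Codes are linked to arm and visit only after the readings are locked.

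The person who reads must not also hold the key, or the masking is nominal.

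The cost is a short protocol addition, a recoding step for at most 14 × 3 = 42 participant-visits, and later availability of the thickness data. Sample size, scans and visits do not change. One limit should be acknowledged: masked reading does not cover image acquisition, where probe placement and pressure are set live at a known visit.

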5 STATISTICS AND METHODOLOGY

5.1. Statistical analysis plan and sample size calculation

A priori sample size calculation was performed using G*power (Version 3.1, Franz Faul, Germany) to determine participants numbers (n) ($\alpha = 0.05$; effect size = 0.46; test family = F test, and statistical test = analysis of variance (ANOVA) repeated measures, within-between interaction; number of groups = 2; number of measurements = 3; power = 0.8) and revealed n = 10 participants. The effect size was estimated based on previous research with a comparable ILEX device in healthy volunteers (Fisher et al., 2018).

Assumption of normality will be verified using the Shapiro-Wilk test. Mauchly's test will indicate the violation of the assumption of sphericity. Normally distributed data will be analysed applying ANOVA repeated measures with within-between interactions to compare the means of each variable over the three repeated observations (within) and between the intervention and sham group (between). Not normally distributed data will be examined using non-parametric statistics (Friedman's two-way ANOVA). Post hoc Bonferroni test correction will be applied. Probability values $p < 0.05$ will be considered statistically significant.

Men and women are included in this study and will be part of the randomization process. The planned sample size of this study does not allow for gender-specific analysis. A gender difference analysis will have to be part of a future study.

Analyses will be performed using RStudio Team (2023) (RStudio: Integrated Development Environment for R. Boston, MA) and IBM SPSS Statistics (Version 27, IBM Corp., Armonk, NY, USA).

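### An under-specified normality pretest can move an outcome from the powered group-by-time ANOVA to Friedman's test, which cannot compare diathermy with sham

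*Combined protocol and SAP*

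**What the plan says.** Section 5.1 sets up a two-way branch. The entry condition is "Assumption of normality will be verified using the Shapiro-Wilk test". On one side, "Normally distributed data will be analysed applying ANOVA repeated measures with within-between interactions". On the other, "Not normally distributed data will be examined using non-parametric statistics (Friedman's two-way ANOVA"). The only significance threshold given is general: "Probability values $p < 0.05$ will be considered statistically significant".

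The sample size in the same section was computed for the within-between interaction alone, with effect size 0.46, alpha 0.05 and "number of groups = 2; number of measurements = 3; power = 0.8"; it "revealed n = 10 participants". Section 4.1 then recruits 14. Section 3.3 gives block randomisation with sex as covariate and no allocation ratio. Section 3.1 lists two primary hypotheses: that training improves strength, and that diathermy improves it more than sham.

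The plan does not say whether raw values, changes from baseline or model residuals are tested. It does not say whether testing is per visit, per arm and visit, or once. Nor does it say what happens when one visit fails and the other two pass.

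**The concern.** The pretest is a switch, not a diagnostic: its result decides whether the powered analysis is run at all. Friedman's test compares the three visits within persons and ignores arm. An outcome sent there has no planned test of the second primary hypothesis or of its counterparts for the secondary outcomes.

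There is also a risk of misreading. Both arms train, so a common rise over time is expected. Friedman's test would probably be significant for that reason, and the result could be taken as evidence about diathermy. Because the details of the pretest are open, they could be settled after the data are seen.

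**Working it through.** **Inputs.** From section 5.1: f = 0.46, alpha 0.05, 2 groups, 3 measurements, power 0.80, n = 10. From section 4.1: 14 participants. Assumed, because the documents are silent: 7 per arm, a 0.05 threshold for Shapiro-Wilk, diversion on any failure, compound symmetry, and a between-visit correlation (rho) varied from 0 to 0.95.

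**Step 1: the plan's own figure.** For the interaction, lambda = f² × N × m / (1 − rho), df1 = (k − 1)(m − 1) and df2 = (N − k)(m − 1). With rho = 0.5 and epsilon = 1 (both assumed), N = 10 gives lambda = 0.2116 × 10 × 3 / 0.5 = 12.70, df 2 and 16, power 0.833. N = 8 gives 0.709, so n = 10 reproduces. N = 14 gives 0.952. This power belongs to the interaction test only.

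**Step 2: diversion of normal data, by hand.** For k independent tests at 0.05 the chance of at least one rejection is 1 − 0.95^k: 14.3% for k = 3 and 26.5% for k = 6.

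**Step 3: the same by simulation.** Exactly normal data, N = 14, no effects, 20,000 runs per row:

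| rho | 3 tests, one per visit (n = 14) | 6 tests, one per cell (n = 7) | 1 test, ANOVA residuals |
|---|---|---|---|
| 0 | 13.6% | 26.2% | 2.8% |
| 0.5 | 14.2% | 27.2% | 2.7% |
| 0.8 | 13.4% | 25.2% | 2.7% |
| 0.9 | 11.1% | 22.7% | 2.7% |
| 0.95 | 10.1% | 20.7% | 2.9% |

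A smaller run (4,000) gave 14.6% for three tests at rho 0.5, hence the range 10-15%. One test on the arm-centred change from BL to F/U2 diverted 4.1-4.7%. The residuals in the last column have person effects removed. Stacking all 14 × 3 = 42 cell-centred values with person effects left in is a poor choice: it diverted 6% at rho 0.5 and 27% at rho 0.9.

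**Step 4: what the fallback detects.** Friedman's test on normal data, N = 14, 5,000 runs per scenario, rho 0.5 and 0.8:
- Equal time effect in both arms (1 SD by the last visit), no interaction: rejects in 77% and 99%.
- Pure interaction (arms 1 SD apart at the last visit, no average change): rejects in 3.5% and 2.0%.

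It responds to training and is blind to the arm difference.

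**Step 5: cost to the between-arm question.** For a between-arm difference of 1.5 SD of the change score, the always-run ANOVA has power of about 65%. With the branch as written, simulation gives about 57% (per visit) or 47-51% (per cell). This fits simple arithmetic, counting a diverted outcome as no detection: 65% × (1 − 0.13) ≈ 57% and 65% × (1 − 0.25) ≈ 49%.

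**Step 6: the switch with a different fallback.** Send diverted outcomes instead to a Mann-Whitney test on the BL-to-F/U2 change. Over rho 0.5-0.9 (4,000 runs each), type I error is 4.7-5.2% with the switch and 4.9-5.6% for the ANOVA always. Power is 32-34% for a 1 SD difference and 65-67% for 1.5 SD, with or without the switch.

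**The case against.** The branch rule is written down in advance, and a normality check before ANOVA is common practice. Friedman's test does address the first primary hypothesis, on training over time. The plan may intend a single check on residuals, in which case only about 3% of normal outcomes would be diverted. All of this is fair. The first two points do not restore a between-arm test to a diverted outcome, and the third rests on something the plan does not say.

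Two stronger readings are tempting and should not be adopted.

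- A reader might infer that the plan tests the wrong quantity several times per outcome, so that a fixed share of roughly 12-26% of normal outcomes is lost. Section 5.1 attaches normality to the data, which makes testing raw visit scores plausible, but it names neither the quantity nor the number of tests. The rates follow mainly from the assumed number of tests. Testing raw scores adds little by itself: with an equal sex split, a sex difference of up to 3 within-sex SD left the per-visit rate between 8% and 17%.
- A reader might infer that the switch does material damage whatever the fallback. Step 6 shows otherwise for normal data. That comparison was not run on non-normal data.

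Nor can one say that the pretest mostly removes valid data, because the documents do not show how many outcomes are truly normal. Its sensitivity is limited at cell level: exponential data are rejected in 28% of samples at n = 7, against 62-63% at n = 14.

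**Conclusion.** The point holds in conditional form. Section 5.1 makes the powered group-by-time analysis depend on an under-specified pretest and sends failures to a test that cannot answer the diathermy-versus-sham question. Under the stated assumptions, about 10-15% (per visit) or 21-27% (per cell) of exactly normal outcomes would lose their between-arm test, against about 3-5% for one test on ANOVA residuals or change scores. For a 1.5 SD difference, power falls from about 65% to about 57% or 47-51%.

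The defect lies in the switch and the Friedman fallback together. The rates rest on equal arms, a 0.05 pretest threshold, diversion on any failure and the assumed correlations, none of which the documents give.

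**What to change.** In section 5.1, drop Shapiro-Wilk as the selector. State that the group-by-time interaction analysis is the primary analysis for every continuous outcome, whatever the normality check shows. Assess normality once, on the model residuals, for example with a Q-Q plot. If it is poor, add a permutation test of the same between-arm contrast as a sensitivity analysis, not as a replacement. The permutations should follow the actual randomisation, that is, both sex and blocks, so the randomisation list must be kept for this purpose. Friedman's test should not stand in for a between-arm comparison.

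The cost is a paragraph of SAP text and a few lines of R, which the plan already names; no extra participants or visits are needed. The downside is small: for a clearly skewed outcome the main p-value relies on the robustness of the ANOVA, and the permutation result would show how far that matters.
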